a) Resting state functional connectivity (LFBF correlation): The time series data pre-processing (physiologic noise reduction, slice-timing correction, realignment, de-trending and bandpass filtering to extract low frequency BOLD fluctuations) will be accomplished using the AFNI software⁸⁷. SPM's (Wellcome Department of Cognitive Neurology, London, United Kingdom) mutual information algorithm will be applied to co-register each subject's high-resolution MPRAGE anatomical image to the mean of all functional connectivity image volumes and segment it into its tissue components. Three mean time-series, calculated by averaging across all brain, white matter and cerebrospinal fluid voxels will be utilized to account for any remaining global effects from each voxel's time series⁸⁸. The measures of functional connectivity will be evaluated on the AFNI pre-processed native-space connectivity volumes. We will either extract correlations between the mean time series of seed regions such as the amygdala and mean time series of another region such as the ventral anterior cingulate or calculate these correlations for all other voxels in the brain and thus generate connectivity maps. The more detailed description of the Pearson correlation coefficient calculation between the averaged LFBF time series of a-priori defined ROIs and its transformation to T-statistic was provided earlier⁴¹. Based on ACC region of the Talairach Daemon⁸⁹, ventral ACC (vACC) is defined as the rostral ventral part of the ACC resembling rostral Brodmann Areas (BA) 24 and 32, the area that has recently been reported to be involved in corticoamygdalar connectivity and mood regulation^{90,91}. The amygdalar ROIs will be defined using MarsBar's Montreal Neurological Institute (MNI) anatomical library definition but 10 mm diameter spherical regions centered at location (-23, -5, -15) and (23, -5, -15) will also be evaluated as adopted from the Talairach Daemon dataset⁸⁹. The medial and lateral OFC ROIs will also be defined from the MarsBar MNI anatomical library. The connectivity map approach used in our preliminary data analyses provides not only a measure of the regional connectivity but also its spatial distribution and can be utilized to fine-tune the seed region location, shape and size. These connectivity maps will be normalized to a common space by applying segmentation-generated transformation matrix, interpolated to 2 mm per side isotropic voxels and smoothed by a 6 mm full-width half-maximum (FWHM) Gaussian kernel. The resulting connectivity maps will be entered into SPM's second-level models (full factorial or paired-T design) to visualize as well as quantitate between-group differences. It should be noted that seed regions will be defined in the MNI space but that native-space ROIs will be checked using SPM's check-registration feature by overlaying them onto each subject's high-resolution anatomical and functional connectivity volumes. This procedure will detect low signal regions and normalization problems. Beside the above ROI seed based hypothesis driven analysis we will also explore other potential methods to conduct pattern analysis using independent and principal components analysis^{74,92}.

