Specific Aim 1: Differentiation between BDD and UD: We will conduct a one way ANOVA with the connectivity and activation measures as dependent variables to look at differences between groups (BDD and UD). The analyses will be similar to those in our previous studies^{41, 42}. The normality assumptions will be examined using the Kolmogorov-Smirnov test. Box-Cox type transformation methods will be employed if the normality assumption is violated for the outcome variable. To adjust for multiple comparisons accounting for multiple brain ROIs and ad-hoc comparisons conducted within an ANOVA model, Bonferroni adjustment will be used to control overall type I error rates (over-all significance level will be set to 0.05). A post ANOVA logistic regression based classification model will be constructed to build a classifier between BDD and UD. Specificity and sensitivity will be examined using receiver operating characteristics (ROC) curves. We will use leave-one out cross validation method to assess predictive performance of our classification model⁹⁶.

Specific Aim 2: Differentiation between BDD, HRUD, LRUD and healthy control: We will use corticoamygdalar connectivity, amygdalar-LOFC connectivity and ACC Activation in Emotion to perform one-way ANOVA among all four groups. Prior to the analysis, each of these variables will be transformed (using the Box-Cox transformation) so that they will made as close to Gaussian as possible. The normality assumptions will be examined using the Kolmogorov-Smirnov test. Specificity and sensitivity will be examined as in Aim 1.

Specific Aim 3: Identification of imaging measures significantly affecting the rate of conversion from UD to BD: The conversion of UD subjects into BDD is defined as the time to event phenomenon and will be modeled using Cox-proportional hazard model given by,

$$\log(h(t)) = h_0(t) + \beta_1 X_1 + \beta_2 X_2 + \dots + \beta_p X_p$$

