Adjusting for covariates: These include behavioral rating such as, attentional variables such as response time, and accuracy of response, and changes in physiological ratings; demographic variables such as age, gender, and ethnicity; scores on behavioral measures such as anxiety; treatment with concomitant medications such as atypical neuroleptics during the study; treatment history, substance abuse, and trauma history; and structural variables such as whole brain and ROI volumes. We will first identify the covariates with highly correlated with the outcome measures. Next, from this pool of highly correlated covariates to guard against multicollinearity and to conserve for degrees of freedom to ensure that we have sufficient power. To control for potential confounding effects from these covariates and not over-fit in any of our models, we will use the forward stepwise regression model building approach - so that only one covariate will be included at a time in the model - which allows us to screen out covariates that are not related to our outcome measures by using an elevated p-value ($p=0.1$) and reserve statistical power to a limited number of variables that are shown to be associated with outcome measures in our data⁹⁸.

2c(ii)lb. Sample size and power consideration: Preliminary data obtained from BDD and UD subjects were compared with healthy subjects to obtain estimates of sample size at significance level set at 0.05. Proc Power of SAS software is used to estimate the sample size.

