3. HUMAN SUBJECTS

E1a. Human Subjects Characteristics:

The human subjects age range 16 - 30 yrs (inclusive) involved in this study will be - 40 BDD, 60 HRUD, 60 LRUD and 40 healthy control subjects matched as a group for age, gender and ethnicity who will be studied at baseline. BDD and UD subjects will be matched for depression severity at the time of the scan. However, it is likely that, by definition the BDD and UD subjects will be different in terms of other illness characteristics such as duration of illness, number of episodes, and history of alcohol and substance abuse. We will treat those illness variables as covariates in our statistical analysis (as described in section 2c(ii)1a above) to take into account the potential confounding effects of some of these variables.

Inclusion criteria for BDD patients:

1. Ages 15 - 30 years (inclusive) and able to give voluntary informed consent (consent will be taken from both parents and child for children under the age of 18)
2. Satisfy criteria for Diagnostic and Statistical Manual 4th edition (DSM-IV-TR) for Bipolar I or II disorder
3. Satisfy criteria for DSM-IV depressive episode-current
4. 17-item Hamilton Depression Rating Scale > 15 but < 25;
5. Young Mania Rating Scale score < 10
6. Satisfy criteria to undergo an MRI scan based on MRI screening questionnaire.
7. Able to be managed as outpatients during the study as ascertained by the following –
 - i. Clinical Global Severity Scale < 5 i.e. moderately ill;
 - ii. No significant suicidal or homicidal ideation or grossly disabled.

Inclusion criteria for All UD patients:

1. Ages 15 - 30 years and able to give voluntary informed consent (consent will be taken from both parents and child for children under the age of 18).
2. Satisfy criteria for DSM-IV-TR Major Depressive Episode using a Structured Interview
3. Never met criteria for mania or hypomania
4. 17-item Hamilton Depression Rating Scale score (HDRS) > 15 and < 25.
5. Young Mania Rating Scale (YMRS) score < 10
6. Satisfy safety criteria to undergo an MRI scan
7. Able to be managed as outpatients during the study as ascertained by the following –
 - i. Clinical Global Severity Scale < 5 i.e. moderately ill;
 - ii. No significant suicidal or homicidal ideation or grossly disabled

Additional Inclusion criteria for High Risk UD (HRUD) patients beside the inclusion criteria for UD:

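### Does the unlisted predictor set of the BDD-versus-UD classifier make its leave-one-out accuracy optimistic?

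*Combined protocol and SAP*

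**What the plan says.** All references are to the combined protocol and SAP.

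- **Section 2c(ii)Ia, Specific Aim 1.** After a one-way ANOVA of the connectivity and activation measures with Bonferroni adjustment, "A post ANOVA logistic regression based classification model will be constructed to build a classifier between BDD and UD". Sensitivity and specificity come from ROC curves, and "We will use leave-one out cross validation method to assess predictive performance of our classification model". There is no predictor list, cut-off rule or target AUC.
- **Section 2c(ii)Ia, Specific Aim 2.** Three measures are named for the ANOVA, and then "Specificity and sensitivity will be examined as in Aim 1".
- **Section 2c(ii)Ia, Adjusting for covariates.** The first step is "We will first identify the covariates with highly correlated with the outcome measures". Then, to control confounding and "not over-fit in any of our models, we will use the forward stepwise regression model building approach", with entry at p=0.1.
- **Section 2c(ii)H2, part a.** Amygdala regions come from an anatomical library, but 10 mm spheres "will also be evaluated as adopted from the Talairach Daemon dataset". Connectivity maps "can be utilized to fine-tune the seed region location, shape and size".
- **Section 1, Hypothesis 1, and section 2c(ii)Ib, Aim 1.** Each names three measures: LOFC-amygdala connectivity, (v)ACC-amygdala connectivity and (d)ACC activation on NoGo-Go. The pilot effects are 0.27, 0.482 and 0.726.

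**The concern.** Leave-one-out gives an honest accuracy estimate only if every step that uses the diagnosis label is redone without the left-out subject. The plan does not say this. Its stepwise rule refers to all of its models, and in the classifier the outcome is the diagnosis itself. Read literally and run once on 160 subjects, the rule would let each left-out subject's label help choose the model that is then tested on that subject. Having two amygdala definitions, two hemispheres and adjustable seeds adds further choices.

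Telling BDD from UD is the study's overall aim, so an inflated AUC or sensitivity would overstate the main baseline result. The Aim 2 accuracy figures would inherit the problem.

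**Working it through.** The plan gives no AUC, sensitivity or specificity for the classifier, so there is no figure to reproduce. The check has two parts: what the text implies, and how large the bias is under each reading.

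**1. Which predictors?** The Aim 1 paragraph analyses the connectivity and activation measures and then builds the classifier from that ANOVA. Hypothesis 1, the Aim 1 power paragraph and the Aim 2 analysis each name three measures. The natural predictor set is therefore those three.

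**2. Does the stepwise rule reach the classifier?** It sits under covariate adjustment and aims to control confounding. The Aim 1 paragraph uses outcome variable for the imaging measure whose normality is tested. Section 2c(ii)G puts prior medication and substance use into an ANCOVA, and E1a treats illness history as a confounder. All this fits models with imaging outcomes. The wording about any model leaves the other reading possible.

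**3. Inputs for the size.**
- 40 BDD and 120 UD, from the power section.
- Pilot effects 0.27, 0.482 and 0.726, taken as standardised differences between independent normal measures (an assumption).
- Number of noise covariates: the list is open-ended. The covariate paragraph names about 13 kinds and other sections add 5, giving 18. Removing four expected to differ, three matched and one during-study medication leaves 18 − 8 = 10. Both counts are assumptions.
- Selection once on all subjects, forward entry at p<0.1, the three imaging measures always kept.

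**4. Benchmark.** The combined separation is √(0.27² + 0.482² + 0.726²) = √0.832 = 0.912, so the best possible AUC is Φ(0.912/√2) = 0.74. Coefficients estimated from 160 subjects bring the true AUC to about 0.73. The leave-one-out AUC for the fixed three was 0.710 to 0.714, slightly low rather than high.

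**5. Excess of leave-one-out AUC over true AUC when the stepwise rule is applied to the classifier** (simulation, standard error about 0.004):

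| Screen before stepwise entry | 10 candidates | 18 candidates |
|---|---|---|
| None | +0.019 | +0.038 |
| p<0.05 | −0.002 | +0.022 |
| Absolute correlation ≥ 0.2 | −0.009 | −0.003 |
| Absolute correlation ≥ 0.3 | −0.019 | −0.014 |

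The screen matters because few noise variables survive it. With n = 160, t = r√158/√(1 − r²). For r = 0.2 this is 2.57 (p = 0.011), so 10 × 0.011 = 0.11 or 18 × 0.011 = 0.20 noise variables pass on average. With entry at p<0.1 and no screen, roughly 1.0 or 1.8 would pass.

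**6. Other readings.**
- Five noise candidates, no screen: 0.722 against 0.720.
- Bonferroni ANOVA as the only gate: 0.704 against 0.703.
- Covariates screened on the imaging measures instead of the label: 0.703 − 0.718 = −0.015 (10 candidates) and 0.691 − 0.708 = −0.017 (18).

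**7. Seeds and regions.** Section 2c(ii)H2 opens by requiring image analysis without knowledge of group, so seed tuning under that blind cannot use the label. Blinding does not cover picking the best region variant after the ANOVA. For the best of four variants per connectivity measure, the excess was +0.012, +0.006 and −0.005 at inter-variant correlations of 0.5, 0.7 and 0.9.

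**The case for a change.** The strongest case for a change is that a reader cannot tell which reading applies, and the readings give different accuracy figures. With no pre-screen, sensitivity at 80% specificity reads 0.524 against a true 0.479 with 10 noise candidates (4.5 points) and 0.540 against 0.459 with 18 (8.1 points). At the plan's attrition sizes (32 and 96) the unscreened AUC excess is 0.025 and 0.05. The plan also expects that "by definition the BDD and UD subjects will be different in terms of other illness characteristics". If illness history entered the classifier, the AUC would no longer be an imaging result: with four covariates truly differing by 0.3 or 0.5 SD (assumed) and no imaging signal, it would read 0.64 or 0.74. A cut-off picked from the leave-one-out ROC is mildly optimistic even for the fixed three (sensitivity 0.70 against 0.65).

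What stands is the omission itself, and the general principle that label-using steps belong inside the folds. The larger figures do not carry over to the plan as written. They leave out its first screening step, and the 8-point figure needs 18 pure-noise candidates, which conflicts with the plan's own expectation that several truly differ. When four do differ, the stepwise model is no worse than the fixed three (true AUC −0.001 or +0.058 relative to them). The illness-history and cut-off points concern how a result is labelled and reported, which an analyst would ordinarily handle.

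**Conclusion.** No change to the plan follows. The predictor list and fold rule are unwritten, but the text supports the three Hypothesis 1 measures, and with those fixed the leave-one-out AUC is not optimistic. A material bias needs three things together: the covariate rule applied to the classifier, selection run once on all subjects, and the plan's own correlation screen skipped or set loosely. Even then the AUC excess is about 0.02 to 0.04 at the planned sizes. With the screen it is about 0 to 0.02 at p<0.05, and absent at an absolute correlation of 0.2 or more.

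These sizes rest on assumed candidate counts (10 and 18), assumed screen thresholds (the plan does not define a high correlation), independent normal predictors, and pilot effects read as standardised differences. No stated figure is shown to be wrong. No target AUC or go/no-go rule depends on the ROC, and the plan itself says, under Exploratory Aim 3, that validation must come from prospective data.

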HYPOTHESIS 1: BDD subjects will be differentiated from UD and HC subjects on measures of resting state corticoamygdalar connectivity and task-induced activation: BDD subjects will have lower lateral orbitofrontal (LOFC)-amygdalar connectivity but higher ventral anterior cingulate cortex (vACC)-amygdalar connectivity compared to UD and HC subjects. On measures of activation, while performing a happy emotion NoGo-Go task, UD subjects will have less dorsal ACC (dACC) activation compared to BDD and HC subjects.

SPECIFIC AIM 2: To investigate similarities and differences between BDD, HRUD and LRUD on measures of corticoamygdalar connectivity and activation.

HYPOTHESIS 2: HRUD subjects will display a pattern of corticoamygdalar connectivity and task-induced activation which will have similarities and differences with both BDD and LRUD subjects: HRUD subjects will have lower LOFC-amygdalar connectivity similar to BDD subjects but also lower vACC-amygdalar connectivity similar to LRUD subjects. On measures of activation, on the happy emotion NoGo-Go task, HRUD and LRUD subjects would have a similarly decreased dACC activation but on a negative facial emotion recognition task both HRUD and BDD will have lower insula activation compared to LRUD subjects.

EXPLORATORY AIM 3: Ultimately, only prospective data regarding which patients actually develop BD can validate the ability of the baseline imaging measures to predict a BDD or UD diagnosis. The main indicator of bipolarity is the presence of hypo(manic) symptoms. Beside conversion to (hypo)mania we will also measure occurrence of episodes of sub-threshold hypomania symptoms using the Young Mania rating Scale (YMRS) and the mania syndrome checklist of the Schedule for Depression and Schizophrenia (MSC-SADS) which has been recently used to study hypomania development in depressed patients. Besides looking at differences between converters and non-converters, an analysis will also be conducted of the correlation between peak change of YMRS and MSC-SADS scores as well as the slope of the change for mania symptoms ratings obtained over the course of the two years of follow-up. The data could be used to plan future large scale definitive studies.

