
b) Regional Activation Analysis: Functional image volumes in NoGo-Go task will be processed using SPM standard individual first level modeling. Group effects will be obtained using a second level analysis within SPM. Furthermore, a priori defined ROIs will be used to extract mean activation effects for between-group statistical analyses and to collect ROI percent signal change in response to various emotional and non-emotional NoGo-Go conditions. The primary contrast for analysis would be Happy NoGo-Go and Sad NoGo-Go compared to letter NoGo-Go to measure regional brain activation specifically for response inhibition to emotional stimuli. Corrections for multiple comparison/multiple hypothesis will be performed using the false discovery rates⁹³.

c) Volumetric Analysis: While structural analysis is not part of the aims of this proposal we will conduct structural analysis on the high-resolution anatomical scan to explore correlations with functional measures of activation and connectivity. A semiautomated cortical reconstruction and volumetric segmentation will be

performed as previously reported by the investigators⁹⁴ with the Freesurfer image analysis suite⁹⁵. This process generates individual regional measures for cortical and subcortical anatomic structures. We will register individual maps to a standardized atlas and will apply a GLM approach to compare morphometric features across individual subjects and between study groups.

2c(ii)la. Statistical Analysis:

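### Aim 2's stated group test does not locate HRUD between BDD and LRUD, leaves insula activation out, and gives the 'similar' claims no inferential basis

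*Combined protocol and SAP*

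**What the plan says.** Hypothesis 2 (section 1, Specific Aims) places HRUD measure by measure. On connectivity, "HRUD subjects will have lower LOFC-amygdalar connectivity similar to BDD subjects but also lower vACC-amygdalar connectivity similar to LRUD subjects". On the happy NoGo-Go task, "HRUD and LRUD subjects would have a similarly decreased dACC activation". On the negative face task, HRUD and BDD are both predicted to show less insula activation than LRUD.

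The Aim 2 paragraph of section 2c(ii)la, Statistical Analysis, reads "We will use corticoamygdalar connectivity, amygdalar-LOFC connectivity and ACC Activation in Emotion" "to perform one-way ANOVA among all four groups", followed by a Box-Cox transformation, a normality check, and "Specificity and sensitivity will be examined as in Aim 1". It names no contrast, multiplicity rule or equivalence margin.

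Two multiplicity statements stand elsewhere. Under Aim 1, "Bonferroni adjustment will be used to control overall type I error rates", with the scope given as "accounting for multiple brain ROIs and ad-hoc comparisons conducted within an ANOVA model". In section 2c(ii)H2(b), Regional Activation Analysis, "Corrections for multiple comparison/multiple hypothesis will be performed using the false discovery rates". Section 2c(ii)lb, on sample size, quotes power for one pairwise Aim 2 comparison, HRUD vs LRUD on left LOFC-amygdala connectivity, at alpha 0.05.

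**The concern.** The null hypothesis of a four-group ANOVA is that all four means are equal. Hypothesis 2 is about a pattern among three of them. The F test can reject because healthy controls (HC) differ from all patients, which says nothing about HRUD. Followed as written, the plan could report a significant Aim 2 result with Hypothesis 2 false.

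Two parts of the hypothesis are more exposed. The insula prediction has no stated Aim 2 analysis: insula is missing from the measure list, and the Regional Activation Analysis text describes first-level processing for the NoGo-Go task only. The similarity statements have no margin, equivalence test or closeness contrast. Without one, the easy route is to read a non-significant difference as likeness, which these group sizes do not justify.

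**Working it through.** **Inputs.** Group sizes are BDD 40, HRUD 60, LRUD 60 and HC 40 (section 2c(ii), Methods and Design). The HRUD-LRUD effect size is -0.254, with 88% power at 60 per group and alpha 0.05 (section 2c(ii)lb). Differences below are in units of a common SD and tests are two-sided; both are assumptions, because the plan states neither the effect-size scale nor the sidedness.

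**The plan's own figure.** For 60 per group, SE = sqrt(2/60) = 0.183.
- Read as a standardized difference, 0.254 gives 28% power two-sided and 40% one-sided.
- Read as Cohen's f (d = 2 × 0.254 = 0.508), it gives 79% and 87%.
- The stated 88% needs a standardized difference of about 0.572 (normal approximation), that is, a raw difference of 0.254 with SD 0.254/0.572 = 0.44.

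So 88% is not reproduced from what is printed, but it is not shown to be wrong either, since the SD is not given. I use 0.572 below as an illustrative effect because it is the one that makes the plan's figure true.

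**Does the F test separate the patterns?** Noncentrality is λ = Σ nᵢ(μᵢ − μ̄)², with 3 and 196 df and critical F 2.65.
- Only HC differs, by 0.8 SD, and the three patient groups are identical (Hypothesis 2 false): μ̄ = 40 × 0.8/200 = 0.16; λ = 160 × 0.16² + 40 × 0.64² = 20.48; rejection 98%.
- Hypothesis 2 pattern for LOFC (HRUD = BDD; LRUD and HC 0.572 SD higher): μ̄ = 0.286; λ = 200 × 0.286² = 16.36; rejection 93%.

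A simulation of 20,000 runs gave 97% and 94%. Under these assumed effects the test rejects at least as often when Hypothesis 2 is false.

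**Can non-significance show similarity?** The 95% CI half-width is t × sqrt(1/n₁ + 1/n₂).
- BDD vs HRUD: 1.984 × sqrt(1/40 + 1/60) = 1.984 × 0.204 = 0.405 SD.
- HRUD vs LRUD: 1.980 × sqrt(2/60) = 1.980 × 0.183 = 0.362 SD.

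From the noncentral t, the BDD-HRUD comparison is non-significant 51% of the time at a true difference of 0.4 SD and 77% at 0.25 SD. HRUD-LRUD is non-significant 72% of the time at 0.254 SD. The 10% baseline loss that the plan expects would widen the intervals by 1/sqrt(0.9), to about 0.43 and 0.38 SD.

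**Measures side by side.** Hypothesis 2 uses four: LOFC-amygdala, vACC-amygdala, dACC (happy NoGo-Go) and insula (face task). The Aim 2 paragraph lists three. If its general corticoamygdalar term means vACC-amygdala, the first three are covered and insula is not.

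**Power after adjustment, HRUD vs LRUD at 0.572 SD (60/60).**

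| Contrasts in family | Alpha each | Normal approx. | Noncentral t |
|---|---|---|---|
| 1 | 0.05 | 88% | 87% |
| 3 | 0.05/3 = 0.0167 | 77% | 76% |
| 12 (4 measures × 3) | 0.05/12 = 0.0042 | 61% | 58% |

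**A closeness contrast.** HRUD minus the BDD-LRUD midpoint has SE = sqrt(1/60 + (1/40 + 1/60)/4) = 0.165 SD. With HRUD equal to BDD and LRUD 0.572 SD away, the contrast is 0.286 SD, with power 41% at 0.05 and 25% at 0.05/3.

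**The case against.** A reader might infer that Aim 2 has no multiplicity control. The documents do not support that. The Bonferroni sentence sits under Aim 1, but its wording covers follow-up comparisons within any ANOVA. Aim 1's ANOVA is described for two groups, where there are none to make, so the phrase suits a multi-group model better. The false discovery rate statement is not limited to one aim. What remains is that neither rule is tied to Aim 2, the family is undefined, and the two rules are not reconciled. For the same reason, a familywise error near 60% (1 − 0.95¹⁸ for three measures and six pairs) should not be attributed to the plan: it needs 18 independent, unadjusted tests, which nobody planned.

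A reader might also infer that only an omnibus test will be run. That goes too far: the plan adds sensitivity and specificity, SPM second-level group models, and a powered HRUD-LRUD comparison. None of these specifies the Hypothesis 2 contrasts, and classification accuracy does not test the pattern.

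The best objection concerns the word 'similar'. It can be read as a shared direction of abnormality: HRUD and BDD both below LRUD on LOFC connectivity, for example. Ordinary directional contrasts could support that, so it would be wrong to say that half of Hypothesis 2 can never be concluded. The plan also never says that non-significance will be reported as similarity. This narrows the point, but the directional reading still needs contrasts, and none is named.

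**Conclusion.** The concern holds in this form: Aim 2's named group test does not address the position of HRUD, insula activation is left out, the existing multiplicity rules are not tied to Aim 2, and similarity in the sense of closeness has no test. The omission of insula and the absence of contrasts are read directly from the text and need no assumption. The half-widths of 0.41 and 0.36 SD depend on the planned group sizes and a common SD. The 51% figure rests on an assumed 0.4 SD difference, and the 98% and 93% rejection rates on assumed effects of 0.8 and 0.572 SD. Aim 2 is a main aim, not an exploratory one, and the remedy is wording, so the change should be made before the data are analysed.

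**What to change.** In the Aim 2 paragraph:

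1. Add insula activation on the face-emotion task to the measures, and describe its first-level analysis alongside that of the NoGo-Go task.
2. Keep the four-group model with healthy controls. For each Hypothesis 2 measure pre-specify HRUD-LRUD, HRUD-BDD and BDD-LRUD, plus patient group vs HC wherever a reduction is meant relative to controls. BDD-LRUD is needed because Hypothesis 2 asserts it for insula.
3. State that the existing Bonferroni rule (or Holm) applies across these contrasts and measures as one family, and say what the false discovery rate then covers.
4. Report each contrast with its 95% CI, and state that a non-significant difference will not be reported as similarity.
5. Optionally, add HRUD minus the BDD-LRUD midpoint as a secondary estimate with its CI. It shows relative closeness, not equivalence; it is imprecise, and should be read only beside BDD-LRUD, which gives it direction.

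The data and model stay the same; face-task extraction for insula is the only added analysis work. The real cost is the loss of power from stricter thresholds tabulated above, which grows if contrasts with controls join the family. The sample size section should quote power at the adjusted level.
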